## 4. OVERALL STAGE 2 STUDY DESIGN AND PLAN

### 4.1.1. Study Design:

Stage 2: This is a randomized, double-blind Phase 2 study to determine the efficacy and safety of three different doses of PRM-151 in subjects with PMF and post ET/PV MF. Subjects will be randomized to one of three doses: 0.3 mg/kg, 3.0 mg/kg or 10 mg/kg of PRM-151. This is the second stage of an adaptive design study as defined in FDA Draft Guidance for Industry: Adaptive Design Clinical Trials for Drugs and Biologics, February 2010. Modifications to dose levels, schedule, and regimen have been made in Stage 2 based on data from Stage 1.

Approximately 84 subjects with intermediate-1, and intermediate -2, or high risk MF who meet study eligibility requirements will be enrolled and randomized to treatment with single agent PRM-151 at doses of 0.3, 3, or 10 mg/kg IV on Days 1, 3, 5 of Cycle 1 and Day 1 of each subsequent 28 day cycle for nine cycles.

All subjects completing 9 cycles of the originally assigned treatment may switch to an open label extension and receive PRM-151 10 mg/kg every 4 weeks. The first cycle of the open label phase contains a loading dose of 10 mg/kg on days 1, 3 and 5. This will allow for subjects from all three dosing cohorts to receive a loading dose of 10 mg/kg while maintaining the blind.

[figure not shown]
Additionally, subjects who have entered the open label extension study prior to the approval of this amendment may receive a loading dose (10 mg/kg on days 1, 3, and 5), to be administered on their next scheduled cycle after approval of this protocol amendment. This will allow for these subjects to receive any potential pharmacologic benefit of the loading dose.

Enrolled subjects will be considered evaluable for response if they are on study drug for at least twelve weeks.

The Schedule of Events can be found in [APPENDIX A](#).

### 4.1.2. Subject Assignment to Treatment Groups

Subjects will be randomized to one of three doses of PRM-151. The randomization will be stratified according to type of baseline hematologic abnormality (subjects with Hgb < 100g/L and having received  $\geq 2$  units PRBC in the 12 weeks prior to study entry OR subjects with platelet count <  $50 \times 10^9/L$ ) and will ensure that the final study population will include at least 50% of subjects from the second stratum (platelet count <  $50 \times 10^9/L$ ).

### 4.1.3. Study Duration

Each subject will participate in the study for approximately 44 weeks. Participation will include a screening evaluation within four weeks prior to the first PRM-151 administration, nine study cycles of four weeks each, and an end of study visit four weeks after the end of the last cycle.

All subjects may switch to an open label extension utilizing the 10 mg/kg dose after completing 9 cycles of the originally assigned treatment. Subjects may continue with PRM-151 dosing in the absence of disease progression or toxicity warranting discontinuation of therapy. Please see [APPENDIX J](#) for details.

It is estimated that the study will be completed in approximately 18 months.

## 5. STAGE 2 SELECTION OF STUDY POPULATION

### 5.1 Study Population

#### 5.1.1. Inclusion Criteria

This Phase 2 study will enroll up to 111 subjects with MF, 27 in Stage 1, and up to an additional 84 subjects in Stage 2

Each subject must meet all of the following inclusion criteria to be enrolled in the study:

1. Subjects must be  $\geq 18$  years of age at the time of signing the Informed Consent Form (ICF);
2. Subjects must voluntarily sign an ICF;
3. Subjects must have a pathologically confirmed diagnosis of PMF as per the WHO diagnostic criteria (see [APPENDIX C](#)) or post ET/PV MF;
4. At least Grade 2 marrow fibrosis according to the WHO Grading of Bone Marrow Fibrosis ([APPENDIX D](#));
5. Intermediate -1, intermediate -2, or high risk disease according to the IWG-MRT Dynamic International Prognostic Scoring System (see [APPENDIX E](#));
6. A bone marrow biopsy must be performed within four weeks prior to Cycle 1 Day 1 treatment to establish the baseline fibrosis score;
7. Subjects must not be candidates for ruxolitinib based on EITHER:
  - a. Platelet count  $< 50 \times 10^9/L$ , OR
  - b. Hgb  $< 100$  g/L have received  $\geq 2$  units PRBC in the 12 weeks prior to study entry, and be intolerant of or had inadequate response to ruxolitinib;
8. Subjects must have an Eastern Cooperative Oncology Group (ECOG) Performance Status of 0-2. ([APPENDIX F](#));
9. Life expectancy of at least twelve months;
10. At least four weeks must have elapsed between the last dose of any MF-directed drug treatments for myelofibrosis (including investigational therapies) and study enrollment;
11. Recovery to  $\leq$  Grade 1 or baseline of any toxicities due to prior systemic treatments, excluding alopecia;
12. Women of child bearing potential (WCBP), defined as a sexually mature woman not surgically sterilized or not post-menopausal for at least 24 consecutive months if  $< 55$  years or 12 months if  $> 55$  years, must have a negative serum pregnancy test within four weeks prior to the first dose of study drug and must agree to use highly effective methods of birth control throughout the study. Highly effective methods of contraception include combined (estrogen and progestogen containing) hormonal contraception associated with inhibition of ovulation by oral, intravaginal, or transdermal administration; progestogen-only hormonal contraception associated with inhibition of ovulation by oral, injectable, or implantable administration; intrauterine device (IUD); intrauterine hormone-releasing system (IUS); bilateral tubal occlusion; partner vasectomy, and total abstinence (only if

total abstinence is the preferred method and usual lifestyle of the subject). Adequate contraceptive use should be continued until 28 days after the final dose of the study drug.

13. Ability to adhere to the study visit schedule and all protocol requirements;
14. Must have an adequate organ function as demonstrated by the following:
  - ALT (SGPT) and/or AST (SGOT)  $\leq 3$  x upper limit of normal (ULN), or  $\leq 4$  x ULN (if upon judgment of the treating physician, it is believed to be due to extramedullary hematopoiesis [EMH] related to MF);
  - Direct bilirubin  $\leq 1.5$  x ULN; or  $\leq 2$  x ULN (if upon judgment of the treating physician, it is believed to be due to EMH related to MF);
  - Serum creatinine  $\leq 2.5$ x ULN.

### 5.1.2. Exclusion Criteria

Subjects meeting any of the following exclusion criteria are not to be enrolled in the study:

1. White blood cell count  $> 25 \times 10^9/L$  or  $> 10\%$  peripheral blood blasts;
2. Other invasive malignancies within the last 3 years, except non-melanoma skin cancer and localized cured prostate and cervical cancer;
3. History of stroke, unstable angina, myocardial infarction, or ventricular arrhythmia requiring medication or mechanical control within the last 6 months;
4. Presence of active serious infection;
5. Any serious, unstable medical or psychiatric condition that would prevent, (as judged by the Investigator) the subject from signing the informed consent form or any condition, including the presence of laboratory abnormalities, which places the subject at unacceptable risk if he/she were to participate in the study or confounds the ability to interpret data from the study;
6. Known history of human immunodeficiency virus (HIV), or known active hepatitis A, B, or C infection;
7. Organ transplant recipients other than bone marrow transplant;
8. Women who are pregnant or lactating.

## 6. STAGE 2 STUDY TREATMENT(S)

### 6.1. Investigational Product

PRM-151 will be supplied by Promedior as a solution for Injection.

### 6.2. Treatment(s) Administered

All subjects will receive intravenous (IV) infusions of 0.3 mg/kg, 3.0 mg/kg or 10 mg/kg PRM-151, with dose based on the subject's weight on Day 1 for Days 1, 3 and 5 of Cycle 1, and all subsequent doses based on the subjects' weight on the first day of each cycle. Subjects will be observed for one hour after each dose. Refer to the Pharmacy Manual and the Investigator's Brochure for detailed instructions on special precautions and handling.

PRM-151 will be held for any treatment emergent Grade 3 non-hematologic or any Grade 4 adverse event and resumed when adverse event has resolved to Grade 1 or baseline.

### **6.3. Dose for Each Subject**

Subjects will be randomized to treatment with single agent PRM-151 at doses 0.3, 3, or 10 mg/kg IV administered as a 60 minute intravenous infusion on Days 1, 3, and 5 of Cycle 1 and Day 1 of each subsequent 28 day cycle for nine cycles.

For OLE dosing refer to Appendix J.

### **6.4. Method of Assigning Subjects to Treatment Groups**

Subjects will be randomized to treatment cohorts in a double-blind fashion. Randomization will be accomplished using an interactive response system (IRS). The IRS will contain the randomization schedule. At the screening visit, the investigative site will contact IRS. The site will enroll the subject into the IRS by indicating minimal information to sufficiently distinguish one subject from another and will receive the subject ID number. At the Cycle 1, Day 1 visit, the unblinded pharmacist (or designee) will access IRS to randomize the subject. The system will associate that subject with the next available treatment on the randomization schedule. IRS will inform the unblinded pharmacist (or designee) to which PRM-151 dose the subject has been assigned.

The unblinded pharmacist will contact IRS at each dosing visit. The randomization schedule allows for overage, such as enrollment, which will be controlled by IRS and when a sufficient number of subjects have been enrolled, the randomization part of the system will be stopped. The portion of the system that manages re-supply will remain active until the last subject completes the study.

### **6.5. Blinding**

This study will be Subject, Investigator, Assessor (central adjudication panel of expert hematopathologists) and Sponsor-blinded. The site Pharmacist will be unblinded to the dose assignment. Additional details regarding procedures for maintaining the blind can be found in the Pharmacy Manual.

#### **6.5.1. Breaking the Blind**

Blinding should only be broken in emergency situations for reasons of subject safety. Whenever possible, the Investigator should attempt to contact the Promedior Medical Monitor before breaking the blind. When the blind is broken, the reason must be fully documented in the source documents and entered into the eCRF as applicable. At all other times treatment and randomization information will be kept confidential and will not be release to the Investigator/blinded study staff until conclusion of the study.

## **6.6. Concomitant Medications, Therapies and Medical/Surgical Interventions**

Concomitant medications, therapies, and medical/surgical interventions must be documented on the electronic case report form (eCRF) beginning at the signing of informed consent. Subjects are not permitted to receive any treatment for myelofibrosis.

The following concomitant medications are excluded during the study:

- Hematopoietic growth factors, including erythropoietin, G-CSF, GM-CSF, thrombopoietin. Exception: G-CSF may be used as part of the management of febrile neutropenia, and must be documented in the CRF.
- Any therapy that is or may be active against myelofibrosis including JAK kinase inhibitors, chemotherapy, biologics (including antibodies), androgens, radiation therapy, any tyrosine kinase inhibitors (TKIs), any immunomodulatory agents, or investigational agents other than the treatment regimen in this protocol.
- Hydroxyurea is not permitted
- Anagrelide is not permitted
- Steroids, with the exception of prednisone  $\leq 10$  mg po qd at a stable dose for at least three months for a condition unrelated to MF, or as intra-articular injection for an acute problem. If steroids are required for management of an infusion reaction, it will be documented in the CRF.

## **6.7. Treatment Compliance**

PRM-151 is administered under controlled conditions by the Investigator or designee; therefore, full subject compliance with study treatment is anticipated in this study.

## **6.8. Packaging and Labeling**

PRM-151 is supplied in 10 ml single use vials as a clear to opalescent, sterile 20.0 mg/mL solution 10 mM sodium phosphate, 5% (w/v) sorbitol, and 0.01% (w/v) polysorbate 20 with a pH of 7.5. Each vial contains 8 ml PRM-151 (160 mg of PRM-151).

## **6.9. Storage and Accountability**

PRM-151 will be provided to the clinical site in a temperature controlled, monitored container. Investigational product should be stored under refrigerated conditions (2 C-8 C [35.6 °F-46.4°F] and protected from light. Vigorous mixing or vortexing should be avoided.

Investigational product will be dispensed at the study site and stored in a locked storage area. The disposition of all investigational product delivered to a Principal Investigator must be recorded on a subject-by-subject basis by completing the Clinical Trial Material Accountability Log. The date and time of administration of the investigational product must be documented on the appropriate eCRF.

The Principal Investigator, Clinical Research Coordinator, or designee (e.g., Pharmacist) must ensure that all documentation regarding investigational product receipt, storage, dispensing, loss/damaged and return of used/unused product is complete, accurate, and ready for review at each monitoring visit and/or audit. The sites must ensure that the investigational product is available for the monitor to inventory and prepare for return shipment to the Sponsor or designee, if required.

All packing slips and other shipment documentation must be retained as well as any investigational product return forms.

See the Pharmacy Manual for additional details.

## **7. STUDY PROCEDURES**

Detailed descriptions of subject evaluations required for this protocol are described in this section. These evaluations will be performed during the indicated days and weeks of the study as described in Stage 2 Study Activities and in the Schedule of Events table in [APPENDIX A](#).

Subjects enrolled in the open-label extension protocol of Stage 1 will continue to follow the study procedures outlined in [Appendix L](#).

Subjects following Stage 2 extension protocol should continue to follow the study procedures outlined in [Appendix J](#).

All data collected are to be recorded on the appropriate eCRF page.

The Investigator at the clinical trial site is responsible for maintaining a record of all subjects pre-screened, screened, and enrolled into the study.

### **7.1. Informed Consent**

Prior to conducting any study-related procedures, written informed consent must be obtained from the subject or the subject's legally authorized representative.

The nature, scope, and possible consequences, including risks and benefits, of the study will be explained to the subject by the Investigator or designee in accordance with the guidelines described in Section 11.4. Documentation and filing of informed consent documents should be completed according to Section 11.4.

### **7.2. Study Entrance Criteria**

At Screening, each subject will be reviewed for eligibility against the study entrance criteria. Subjects who do not meet the study entrance criteria will not be allowed to participate in the study. The reason(s) for the subject's ineligibility for the study will be documented. All subjects must undergo a bone marrow biopsy for grading of bone marrow fibrosis. Subjects with a myelofibrosis Grade < 2, according to the WHO criteria ([APPENDIX D](#)), as determined by the local pathologist, will not be allowed to participate in the study.

### **7.3. Confirmation of Study Eligibility**

Subject eligibility according to the study inclusion and exclusion criteria will be confirmed at study entry on the basis of review of the study entrance criteria.

### **7.4. Demographics**

Subject demographic information including gender, age, date of birth, race, ethnicity and number of years since diagnosis of MF will be collected prior to the subject receiving the first dose of PRM-151.

### **7.5. Medical History**

Medical history will be recorded in the eCRF. Any relevant and/or significant previous or existing medical condition(s) that occurred within 5 years prior to time of informed consent should be reported as medical history. Prior therapies for myelofibrosis will be recorded in the eCRF. Transfusion history and complete blood counts for three months prior to screening, and between screening and first dose, will be recorded in the eCRF. Results of prior bone marrow biopsies will be collected and recorded in the eCRF.

### **7.6. Height and Weight**

Height and weight will be recorded for all subjects.

### **7.7. Eastern Cooperative Oncology Group Performance Status**

Performance status will be assessed following the Eastern Cooperative Oncology Group (ECOG) scoring system ([APPENDIX F](#)).

### **7.8. Investigational Product Administration**

Medical personnel authorized by the Investigator will be responsible for the administration of study drug and for observation of each subject throughout the study.

Subjects will receive PRM-151 administered as a 60 minute intravenous infusion at a dose of 0.3 mg/kg, 3.0 mg/kg, or 10 mg/kg on Days 1, 3 and 5 of Cycle 1 and Day 1 of each subsequent 28 day cycle for nine cycles.

Subjects responding to treatment with PRM-151 may continue to receive it as long as there is benefit. Please see [APPENDIX J](#) for details.

In the case of Grade 2 occurrence of signs and symptoms consistent with infusion related reaction, follow institutional protocol and reduce the rate of infusion of PRM-151 to half the initial rate; consider discontinuing infusion of PRM-151 if symptoms do not respond to medical intervention. If signs and symptoms resolve with intervention including discontinuation of PRM-151, PRM-151 infusion may be restarted at half the initial rate.

In the case of Grade 3 or greater occurrence of signs and symptoms consistent with infusion related reaction, discontinue infusion of PRM-151.

If PRM-151 resulted in signs consistent with Grade 2 or 3 infusion related reaction, during a prior administration, infuse PRM-151 over 1 hour and use the following premedication for all subsequent PRM-151 administration:

- a. Diphenhydramine 50 mg IV or clemastine 2 mg IV or an equivalent dose of an antihistaminic drug
- b. Dexamethasone 10 mg IV or equivalent corticosteroid

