Infusion reactions were reported in two subjects in Stage 1 of this study. In the event of acute hypersensitivity or other infusion reaction, institutional protocol should be initiated and a blood sample drawn for anti-PTX-2 antibodies and cytokines. Signs and symptoms of an infusion reaction may include the following: headache, fever, facial flushing, pruritus, myalgia, nausea, chest tightness, dyspnea, vomiting, erythema, abdominal discomfort, diaphoresis, shivers, hypertension, hypotension, lightheadedness, palpitations, urticaria and somnolence. Although unlikely, serious allergic reactions (e.g., anaphylaxis) may occur at any time during the infusion.

In the case of Grade 2 occurrence of signs and symptoms consistent with infusion related reaction, follow institutional protocol and reduce the rate of infusion of PRM-151 to half the initial rate; consider discontinue infusion of PRM-151 if symptoms do not respond to medical intervention. If

signs and symptoms resolve with intervention including discontinuation of PRM-151, PRM-151 infusion may be restarted at half the initial rate.

In the case of Grade 3 or greater occurrence of signs and symptoms consistent with infusion related reaction, discontinue infusion of PRM-151.

If PRM-151 resulted in signs and symptoms consistent with Grade 2 or 3 Infusion related reaction, infuse PRM-151 over 1 hour and use the following premedication for all subsequent PRM-151 administration:

- a. Diphenhydramine 50 mg IV or clemastine 2 mg IV or an equivalent dose of an antihistaminic drug
- b. Dexamethasone 10 mg IV or an equivalent corticosteroid

Infusion related reactions must be reported to Promedior as described in section 7.13.2.1.1, Reporting of Adverse Events of Special Interest.

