**Table 3: Adverse Event Grading**

Severity	Definition
Grade 1	Mild; asymptomatic or mild symptoms, clinical or diagnostic observations only; intervention not indicated.
Grade 2	Moderate; minimal, local or noninvasive intervention indicated; limiting age-appropriate instrumental ADL.
Grade 3	Severe or medically significant but not immediately life-threatening; hospitalization or prolongation of hospitalization indicated; disabling; limiting self care ADL.
Grade 4	Life-threatening consequences; urgent intervention indicated.
Grade 5	Death related to AE.

**Clarification between Serious and Severe:** The term “severe” is often used to describe the intensity (severity) of a specific event (as in mild, moderate, or severe myocardial infarction); the event itself, however, may be of relatively minor medical significance (such as severe headache). This is not the same as “serious,” which is based on the outcome or action criteria usually associated with events that pose a threat to life or functioning. Seriousness (not severity) and causality serve as a guide for defining regulatory reporting obligations.

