### **7.14. Removal of Subjects from the Trial or Investigational Product**

A subject's participation in the study may be discontinued at any time at the discretion of the Investigator. The following may be justifiable reasons for the Investigator to remove a subject from the study:

- Non-compliance, including failure to appear at one or more study visits;
- The subject withdraws consent;
- The subject was erroneously included in the study;
- The subject develops an exclusion criterion;
- The subject suffers an intolerable adverse event;
- The subject becomes pregnant;
- The study is terminated by the Sponsor.

The subject is free to withdraw consent and discontinue participation in the study at any time without prejudice to further treatment. If a subject discontinues participation in the study, or the subject is discontinued by the Investigator, the Investigator will notify the Sponsor and, when possible, will perform the procedures indicated for the final visit. Follow-up information will be obtained during the final telephone contact, if possible, for subjects who discontinue their participation in or are withdrawn from the study.

Any adverse events (AEs) experienced up to the point of discontinuation must be documented on the AE eCRF. If AE's are present when the subject withdraws from the study, the subject will be re-evaluated within 30 days of withdrawal. All ongoing SAEs at the time of withdrawal will be followed until resolution.

Subjects withdrawn from the study will be replaced at the discretion of the medical monitor and the Investigator. A replacement subject will be randomized to treatment with single agent PRM-151 at doses of 0.3, 3, or 10 mg/kg IV.

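### Read literally, the protocol lets PRM-151 resume after a Grade 4 infusion reaction without the premedication that is mandatory after Grade 2 or 3.

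*Protocol*

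**What the plan says.** Three sections of the protocol govern dosing after an infusion reaction.

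- **Section 6.2, general hold rule.** "PRM-151 will be held for any treatment emergent Grade 3 non-hematologic or any Grade 4 adverse event and resumed when adverse event has resolved". The level required before resuming is Grade 1 or baseline. Infusion reactions are not exempted and Section 7.8 is not cited. The same section sends sites to the Pharmacy Manual and the Investigator's Brochure "for detailed instructions on special precautions and handling".
- **Sections 7.8 and 7.13.1.1, during the infusion.** At Grade 2 the rate is halved, and an infusion that was stopped may be restarted at half rate once symptoms resolve. Above that: "In the case of Grade 3 or greater occurrence of signs and symptoms consistent with infusion related reaction, discontinue infusion of PRM-151". Section 7.13.1.1 adds: "In the event of acute hypersensitivity or other infusion reaction, institutional protocol should be initiated".
- **Sections 7.8 and 7.13.1.1, later doses.** "If PRM-151 resulted in signs consistent with Grade 2 or 3 infusion related reaction, during a prior administration", every later dose is infused over 1 hour after an antihistamine and dexamethasone 10 mg IV or equivalent. Section 7.13.1.1 repeats the rule with the same two grades.

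Table 3 defines Grade 4 as "Life-threatening consequences; urgent intervention indicated". Removal from the study under Section 7.14 is discretionary: "The following may be justifiable reasons for the Investigator to remove a subject from the study".

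**The concern.** The premedication rule covers Grades 2 and 3 and leaves out the most severe reaction a subject can survive. The general rule in 6.2 meanwhile expressly allows dosing to resume after any Grade 4 event. A site following the protocol text alone could re-dose a subject after a life-threatening reaction with no required premedication. A site that stops for good is relying on something the text does not say.

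Suspected infusion reaction is the event the protocol requires to be reported as an adverse event of special interest (Section 7.13.2.1.1), and 7.13.1.1 warns that anaphylaxis may occur during any infusion. The gap carries into the extension. Appendix J has no grade-based reaction rule, gives subjects from all three arms a 10 mg/kg loading course on Days 1, 3 and 5, and in footnote 9 provides for antibody sampling before further infusions after a reaction, without limiting the grade.

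**Working it through.** **Rule trace by grade.** The documents give no figure to reproduce, so the check is to follow each rule in turn.

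| Reaction | During the infusion (7.8, 7.13.1.1) | Between doses (6.2) | Premedication at later doses (7.8, 7.13.1.1) |
|---|---|---|---|
| Grade 2 | Halve rate; may stop and restart at half rate | No hold | Required |
| Grade 3 | Stop the infusion | Hold; resume at Grade 1 or baseline | Required |
| Grade 4 | Stop the infusion | Hold; resume at Grade 1 or baseline | Not triggered |

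**Does stopping the infusion mean stopping for good?** Not on this wording. One sentence covers Grade 3 and above, and Grade 3 then has rules for later doses, so the instruction refers to that infusion. The Grade 2 paragraph also speaks of discontinuing PRM-151 in a case where the infusion may be restarted.

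**What does the later-dose rule add?** Sections 6.3 and 7.8 already set 60 minutes as the standard infusion time, so the 1-hour requirement adds nothing new to it. Premedication is the only added protection, and it is what Grade 4 lacks.

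**Does another provision close the gap?**
- Institutional protocol (7.13.1.1) governs care of the reaction itself.
- Section 7.14 permits removal but does not require it. An intolerable adverse event is one listed ground; another, "The subject develops an exclusion criterion", reaches exclusion 5 (unacceptable risk).
- Section 4.1.3 makes continued dosing conditional on there being no toxicity that warrants stopping, but does not define such toxicity.
- Data monitoring committee review and 24-hour reporting are oversight.
- Section 6.6 allows steroids to manage an infusion reaction. It does not clearly name prophylactic steroid.

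**Amendment log (Appendix M).** The 6.2 resume clause and the premedication text in 7.8 and 7.13.1.1 were both edited in this version. The reason given for the 6.2 edit was hematologic (hemoglobin, platelets). Neither section refers to the other.

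**How often could it arise?** Inputs:
- 27 Stage 1 subjects (Section 5.1.1, taken here as the number treated);
- 2 reactions, both non-serious Grade 2 (Section 1.3), with none reported at Grade 3 or above;
- 15 treated subjects in the multiple-dose IPF study (Section 1.2.3), with no acute infusion reactions (Section 1.4).

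Calculations:
- Any reaction: 2/27 = 7.4%; exact (Clopper-Pearson) 95% CI 0.9% to 24.3%.
- Grade 3 or above, zero events, one-sided 95% upper bound = 1 − 0.05^(1/n):
  - n = 27: 1 − 0.05^(1/27) = 10.5%
  - n = 27 + 15 = 42: 1 − 0.05^(1/42) = 6.9%

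The pooled bound is optimistic. The IPF subjects were dosed only to Day 15, whereas the two Stage 1 reactions came on Days 58 and 225.

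**The case against.** The strongest reply is that 7.8 is graded on purpose. Grade 2 may be restarted, Grade 3 and above may not, and later dosing is provided for only after Grade 2 or 3. Grade 4 is then the one grade with no provision for later dosing, so the natural inference is no rechallenge. On this view the specific section should prevail over the general clause in 6.2, whose latest edit concerned blood counts. That reading is plausible and may be what was intended. It is still only an inference, and 6.2 says the opposite in terms for any Grade 4 event.

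Other points reduce the weight of the concern:

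- The Investigator's Brochure and Pharmacy Manual may hold a Grade 4 rule. This cannot be checked here.
- Premedication after Grade 4 is not forbidden. Each dose is followed by an hour's observation, and few investigators would rechallenge casually after a life-threatening event. These safeguards lower the risk without supplying the rule.
- The 10.5% and 6.9% bounds include Grade 3 reactions, which are already covered, and are driven by small numbers. The 27 is an enrolment figure. They cap how often a severe reaction could occur; they do not give the chance of re-dosing without premedication.
- SAP Section 1 places that plan just before the final database lock of the extensions, so few subjects may still be affected in this trial.

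**Conclusion.** The concern holds. Taken together, Sections 6.2, 7.8 and 7.13.1.1 allow dosing to resume after a Grade 4 infusion reaction with fewer mandated precautions than after Grade 2 or 3, and nothing in the protocol or SAP overrides this.

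The consequence is rare, its probability cannot be derived from the documents, and it has no bearing on any endpoint, error rate or power. It should still be fixed because it concerns a life-threatening event and costs little to correct. The conclusion rests on a literal reading and on there being no Grade 4 rule in the Brochure or Pharmacy Manual. If either contains one, what remains is a missing cross-reference. Confidence is medium for that reason.

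**What to change.** 1. In Section 6.2, exempt infusion-related reactions from the general resume rule and point to 7.8. Restate the Grade 3 hold in 7.8 so that it is not lost.
2. In Sections 7.8 and 7.13.1.1, state that a Grade 4 infusion reaction or anaphylaxis leads to permanent discontinuation of PRM-151. If re-dosing is intended, extend the premedication rule to Grade 2 or greater instead. The choice is a clinical one; either closes the gap.
3. Cross-reference the rule in Appendix J so that it applies in the extension.
4. Optionally, name premedication in the Section 6.6 steroid exception.

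This takes a few sentences in an amendment or, given the stage of the trial, in any follow-on protocol that reuses the wording. It adds no procedures, visits or subjects. The one downside of permanent discontinuation is that a rare affected subject loses the option of further dosing.
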